Pharmacist Management of Attention Deficit Hyperactivity Disorder
Medication Refill Requests

Study Protocol and Statistical Analysis Plan

[name], MPH, [name], [name], PharmD, E. [name], [name], MA, [name], BA, [name], MS, [name], [name], [name]

From The Permanente Medical Group (Division of Research, Virtual Care Team, Adult and Family Medicine regional leads, and TPMG Consulting Services) and Pharmacy Services, Kaiser Permanente Northern California, all in Oakland, CA

Version date: August 27, 2024

NCT06388694

Abstract

Importance. Enhancing the management of messages from patients and providing high-quality, consistent care are top priorities for The Permanente Medical Group (TPMG) and Kaiser Foundation Hospitals/Health Plan (KFH/P). A special extension of the Ryan Haight Act currently enables providers to prescribe controlled substances via telehealth interactions but expires in December 2024. Information about the quality of care provided via telehealth prescribing of controlled substances by pharmacists and primary care physicians would be helpful to inform care delivery within Kaiser Permanente and beyond.

Objective. To compare pharmacist management of refill authorization requests for attention deficit hyperactivity disorder (ADHD) medications with physician management regarding quality of care, efficiency of service, and parent satisfaction.

Design, setting, and participants. This cluster randomized clinical trial will include parents of children in Kaiser Permanente Northern California who request ADHD medication refills via secure messages from April 29 to June 28, 2024. Of KPNC's 63 facilities eligible for inclusion, we will assign 32 to Pharmacist Care and 31 to PCP Care.

Intervention. In the intervention group, a regional team of pharmacists will manage electronic refill authorization requests for ADHD medications using a standard protocol. In the comparison group, pediatricians will manage these visits using a similar protocol.

Main Outcomes and Measures. The primary outcome is whether a patient who did not have a weight recorded in the 6 months before the refill request was referred for a primary care follow-up visit. Secondary outcomes are the days from the secure message request to the prescription order and medication fill, and parent satisfaction.

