The regional pharmacy team started to handle free-text secure message requests for refills from parents of patients with PCPs in pediatrics during a pilot period starting April 11, 2024. Secure messages are different from RARs because they contain free text. These were found to be difficult to flag and send to the regional pharmacy team because accurately identifying the relevant secure messages required manual handling. The rate of such messages that could be identified per day would not have reached the intended sample size for this study. Thus, this study was designed to focus only on RARs, which are much simpler to identify consistently. The regional desktop medicine leader sent an email to the pediatric department at every facility to ask that during the study period, they ignore RARs from facilities randomized to Pharmacist Care, but continue to handle RARs from facilities randomized to Physician Care.

The formal study period will include patients with secure messages sent to the regional pharmacy team from May 6, 2024 to June 21, 2024 (7 weeks). The unit of analysis will be the RAR, allowing some patients to appear up to two times in the study cohort.

4.2. Intervention.

All procedures will be conducted as part of standard of care. In the Pharmacist Care group, each RAR for an ADHD medication will be assigned to a pharmacist on the regional team. Pharmacists will review requests using a standard protocol. They will call parents via telephone to elicit additional information where needed, file ADHD medication prescriptions where appropriate, and send follow-up secure messages.

In the PCP Care group, each ADHD medication RAR will be sent to the PCP. Physicians will review requests using the standard regional protocol (as well as any existing medical center-level protocols). Following this protocol, physicians call patients via telephone to elicit additional information where needed, file ADHD medication refill prescriptions when appropriate, and send follow-up secure messages.

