For the secondary outcomes, we will compare the days from the secure message request to prescription order or medication fill between the Pharmacist Care and PCP Care groups using linear mixed regression models, providing point and interval estimates of between-group differences in mean outcomes. If the numbers of days have a skewed distribution, log transformation will be used. Analyses of other continuous secondary outcomes will be similar. The approach to inclusion of covariates and sensitivity/exploratory analyses is as described for Aim 1.

For patient satisfaction, care experience scores will be compared between the study groups using linear mixed effects regression with log transformation if needed for skewed data, with analyses paralleling that described for the secondary outcomes. For analyses, categorical responses will be combined into a binary variable (Excellent or Very Good vs. Good, Fair, or Poor).

For all aims, secondary analyses will assess variation in the estimates of treatment effect by age, sex, socioeconomic status (using the Neighborhood Deprivation Index), and race and ethnicity, via stratification by level of the potential effect modifier. These stratified analyses will inform the fitting of mixed effects regression models with appropriate cross-product terms between the potential effect modifier and study group indicator variable, allowing for a more formal assessment of heterogeneity in treatment effect.

A facility may drop out before completion of the study if they were assigned to PCP Care but add local pharmacist management, thus diverging from their assigned group. ADHD medication refill requests to such a facility will be censored as of the dropout date (the date that local pharmacist management began).

Tests of significance will be two-tailed with an alpha of .05. No Bonferroni or other formal correction for multiple comparisons will be used, but results will be interpreted with the multiple testing issue in mind.

4.8. Sample size and power. To estimate the available sample, we extrapolated from data analyzed during the pilot period in April 2024.

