Based on initial data in the pilot period, we estimate that the message pool handlers will send the regional pharmacy team 7 secure messages for straightforward ADHD medication refill requests per weekday, i.e., 35 eligible messages per week. We estimate based on expert opinion that 30% of these patients don't have a weight check in the previous 6 months. Assuming a 9-week evaluation period, the estimated sample size is 315 patients, or an average of 5 patients in each of the 63 clusters.

Given the group-randomization study design, calculation of sample sizes and minimum detectable treatment effects must account for the expected intraclass correlation (ICC) of observations within facilities. The ICCs in outcomes of interest are expected to be small, and therefore we present minimum detectable effects for an expected ICC of .03.

For Aim 1, the primary outcome is the % of patients without a weight check in the past 6 months who received referral for an appropriate follow-up visit. The following estimates assume that 30% of the 315 patients with secure messages will have not had a weight check in the past 6

months, for a sample size of 95 (63 clusters with 1.5 patients each). We also assume a desired power of 80%, a two-tailed alpha of 0.05 and an ICC of .03. If 50% of patients in the PCP Care group will receive an appropriate referral, the least detectable difference will 77%. If 80% of the patients in the PCP Care group receive an appropriate referral, the least detectable difference will be 98%. Thus, this sample size yields good power to identify only large differences between the two arms in the primary outcome.

For Aim 2, the outcome is days from the secure message to the prescription order. The following estimates assume a sample size of 315 (63 clusters with 5 patients each), a desired power of 80%, a two-tailed alpha of 0.05 and an ICC of .03. The least detectable effect size for a comparison of means will be 0.334. In other words, this study will have good power to find a statistically significant difference between the Pharmacist Care and PCP Care groups for a small to medium effect size.

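### The sample size of 315 and the detectable effects in section 4.8 come from a 9-week secure-message count, but section 4.1 specifies 7 weeks of RARs, for which no rate is given

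*Combined protocol and SAP*

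**What the plan says.** **Section 4.8 (Sample size and power).** The source of the volume forecast is the pilot: "To estimate the available sample, we extrapolated from data analyzed during the pilot period in April 2024." The rate is "7 secure messages for straightforward ADHD medication refill requests per weekday, i.e., 35 eligible messages per week". Then: "Assuming a 9-week evaluation period, the estimated sample size is 315 patients, or an average of 5 patients in each of the 63 clusters." From 315 the section takes 30% (95) for the primary outcome and 60% (189) for the parent survey. It states detectable rates of 77% against 50% and 98% against 80% (Aim 1), an effect of 0.334 (Aim 2) and an effect of .037 (Aim 3), at 80% power, two-sided alpha 0.05 and ICC 0.03. Appendix A repeats 35 per week, 9 weeks, 315 and 63 clusters, and gives 0.42 for the survey at ICC 0.03.

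**Section 4.1 (Design, setting, and participants).** In the pilot the regional pharmacy team "started to handle free-text secure message requests for refills from parents of patients with PCPs in pediatrics during a pilot period". Of these messages it says: "The rate of such messages that could be identified per day would not have reached the intended sample size for this study." And then: "Thus, this study was designed to focus only on RARs, which are much simpler to identify consistently." The study period runs "from May 6, 2024 to June 21, 2024 (7 weeks"), although that same sentence still speaks of secure messages. The unit of analysis is the RAR, and a patient may contribute two.

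**Abstract.** It includes parents "who request ADHD medication refills via secure messages from April 29 to June 28, 2024".

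**Section 4.5 (Data collection).** Only a patient's first RAR can lead to a survey.

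**The concern.** The forecast in section 4.8 takes both its factors, the rate and the duration, from a design that section 4.1 has replaced. Section 4.1 even judges the identifiable rate of pilot-type messages too low for the intended sample, yet section 4.8 projects its sample from pilot messages. Secure messages and RARs are not two names for one thing: section 4.1 separates them by whether free text is allowed.

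The detectable effects for all three aims rest on this N. As written, a reader cannot tell what the trial could detect. That matters when a null result has to be read, because the Abstract would take similar outcomes in the two arms as support for continuing pharmacist care.

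**Working it through.** **1. Weekdays.** April 29 to June 28, 2024 has 45 weekdays; May 6 to June 21 has 35. So 7 × 45 = 315 and 7 × 35 = 245. The Abstract's dates agree with section 4.8, but section 4.1's do not.

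**2. Method.** N requests in 63 clusters, equal arms, ICC 0.03:
- Design effect: DEFF = 1 + (N/63 − 1) × 0.03.
- Means: detectable effect = 2.8016 × √(4 × DEFF / N), with 2.8016 = 1.96 + 0.8416.
- Proportions: normal approximation with N/(2 × DEFF) per arm, solved for the second rate. Pairs below are unpooled/pooled variance.

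**3. The plan's own figures, from its own inputs.**
- Aim 2: DEFF = 1.12; 2.8016 × √(4 × 1.12/315) = 0.334, as printed.
- Aim 1: 30% of 315 = 94.5, printed as 95. Detectable 0.768/0.775 from 0.50 and 0.976/0.979 from 0.80. Printed: 77% and 98%.
- Aim 3: 60% of 315 = 189; DEFF = 1.06; 2.8016 × √(4 × 1.06/189) = 0.420. Appendix A prints 0.42.

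So the formulas are sound. What fails is the match between the inputs and the design, plus the .037.

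**4. The same formulas for 7 weeks.** The documents give no RAR rate, so the weekly rate is an assumption. Break-even is 315/7 = 45 per week (9 per weekday).

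| RARs per week (assumed) | N | Primary (30%) | Detectable from 50% | Detectable from 80% | Aim 2, SD | Power at the printed Aim 1 and 2 effects |
|---|---|---|---|---|---|---|
| 35 | 245 | 74 | 80–81% | 99–99.5% | 0.373 | 68–73% |
| 45 | 315 | 95 | 77–78% | 98% | 0.334 | 78–83% |
| 60 | 420 | 126 | 74% | 96% | 0.296 | 88–91% |

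These treat repeat RARs from one patient as adding no further correlation.

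**5. Aim 3.** Surveys = 0.6 × N × (1 − share of RARs that are repeats). The repeat share is not given; 20% is an assumption.

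| RARs per week (assumed) | Surveys, no repeats | Effect, SD | Surveys, 20% repeats | Effect, SD |
|---|---|---|---|---|
| 35 | 147 | 0.47 | 118 | 0.52 |
| 45 | 189 | 0.42 | 151 | 0.47 |
| 60 | 252 | 0.37 | 202 | 0.41 |

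With N = 315 and 60% response, 0.42 is reached only if no patient appears twice.

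**6. The .037.** As the survey count grows without limit, 4 × DEFF / N tends to 4 × 0.03/63. The detectable effect therefore cannot fall below 2.8016 × √(4 × 0.03/63) = 0.122. A value of .037 is out of reach, and 0.42/0.037 = 11.4. Reading it as 0.37 does not rescue it: that needs about 250 surveys, and power at 0.37 with 189 is 0.695.

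**The case against.** - **The sums are right, and N was a forecast of available volume, not a recruitment target.** Both true. But a correct calculation on the wrong message type and duration still does not describe the trial.
- **RARs are probably more numerous.** Section 4.1 hints at this, since it turned to RARs after finding too few identifiable secure messages. It gives no number. The shorter period alone lowers N by 22% (245 against 315), and RARs make that up only at 45 or more per week. The 35-per-week row is therefore an illustration, not a prediction.
- **Section 4.8 calls the 315 patients and parents, so 189 already counts people.** The label says so, but 315 is built from a count of messages, and section 4.1 analyses RARs with repeats allowed. The first-RAR point stands; the 20% share is only illustrative.
- **The .037 is an evident misprint.** Probably so: the next sentence in section 4.8 speaks of medium effects, and Appendix A has 0.42. It still needs correcting, and moving the decimal point does not do it.
- **Near 100% the normal approximation is poor.** This is fair. With about 37 per arm, a rate of 99–99.5% implies fewer than 0.4 expected non-events in that arm. Read that cell as almost no room left to show a difference.
- **Other contradictions bear on the same figures.** Section 4.8 speaks of 315 parents in each group but 189 surveys in total; 315 per group would give 378 surveys and 0.309 SD. Section 4.5 surveys a random sample, section 4.8 everyone. Appendix A's proportion rows (0.663 and 0.915 at ICC 0.03) use all 315, not the 95 in the primary analysis. These add to the point and belong in the same correction.
- **Accrual was over by the version date.** This limits the consequence to reporting. It does not make the figures right.

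**Conclusion.** The concern holds and should be fixed. The sample size of 315 and the Aim 1 and 2 detectable effects follow correctly from section 4.8's inputs, but those inputs contradict section 4.1 on message type and duration. Without an RAR rate the net direction of error cannot be known: below 45 RARs per week over 7 weeks the detectable effects are larger than printed, above it they are smaller. Across an assumed 35 to 60 per week, the Aim 2 effect runs from 0.373 to 0.296 SD and the detectable primary rate against 50% from about 81% to 74%.

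For Aim 3, 60% of all RARs is an upper bound on surveys at the planned response rate, and section 4.8 understates the detectable effect about 11-fold relative to Appendix A. The .037 error does not depend on the RAR rate. All results keep the plan's ICC of 0.03, 30% primary share, 60% response and equal arms.

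**What to change.** 1. Reconcile the study dates and the message type (secure message or RAR) across the Abstract, section 4.1 and section 4.8.
2. Restate N and the detectable effects in section 4.8 and Appendix A from an RAR rate and the reconciled duration. If no rate is available, show a range labelled as an assumption on both sides of 45 per week over 7 weeks, for example 35 to 60. Put Appendix A's proportion rows on the primary-outcome subset.
3. For Aim 3, base the survey count on first RARs (distinct patients). State whether all parents or a sample are approached, and whether the total is per group or overall. Replace .037 with the recalculated value.

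The cost is text and recalculation only. The version date (August 27, 2024) falls after both stated end dates, so accrual, estimands and tests do not change. The restated Aim 1 and 2 effects may be less or more favourable than those printed.

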4.4.2. Predictors and covariates

The primary predictor is study group, i.e. Pharmacist Care or PCP Care. Covariates are other variables that could potentially mediate, moderate, or confound the association between the primary predictor and the outcomes. In this study, covariates include patient age, sex, race, ethnicity, language spoken, and comorbidities, as well as the patient's neighborhood-level SES.

4.5. Data collection.

The primary outcome will be measured via analysis of EHR records and chart review, as defined above.

For the secondary outcomes that involve medication prescription orders and fills, and for the exploratory outcomes, we will use data available from KPNC computerized sources, including HealthConnect (HC, aka EPIC) EHR data (from Clarity) and EPIC access logs. For each patient with a refill request, EHR data will be used to identify all ADHD medication prescriptions ordered and filled (sold) during the study period.

Patient care experience will be evaluated by surveying a sample of parents selected at random in both the Pharmacist Care and PCP Care groups. We have designed a short survey that takes no more than 5 to 10 minutes to complete. The survey will be fielded by email, mail, and telephone. Due to the fact that we are asking about a specific care experience and patients' recall fades quickly after 2 weeks, we will field the survey using all 3 modes in a relatively efficient sequence. A letter containing a description of the study, language regarding informed consent and confidentiality, and the survey will be sent by mail on day 7 after the secure message has been replied to, and an email with a link to the online version will be sent on day 11. Telephone administration will be attempted (up to 4 attempts total) starting on day 14 for those who have not replied to the paper or online survey. Only the first RAR will be eligible to generate a survey request. A gift card valued at \$10 to thank patients for considering participation will be included in the mailing. Responses will be treated as confidential and data will be aggregated, with no individual identifiers associated with data presented in reports.

Parent-reported outcomes will be reported on a 5-point scale and will include:

- a. Perceived effectiveness of the initial reply in addressing the request
- b. Perceived quality of care for the request overall

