For Aim 3, the outcome is perceived quality of care on the parent survey, measured on a 5-point Likert scale. We will attempt to survey all 315 parents in each of the two study groups. We estimate a response rate of 60%, for a completed sample of 189 across groups. The outcomes, effectiveness and quality scores, are measured on a continuous 5-point scale. This sample size will yield 80% power to detect effect sizes of .037 (relative to a standard deviation of 1). Thus, the survey will have good power to identify medium sized differences in perceived effectiveness and quality of care.

4. Projected Impact

This study's findings quality and timeliness of care and patient satisfaction will inform decisions about how to deploy pharmacist effort for KPNC. The study leaders include regional leaders for Virtual Medicine and Pharmacy who are well-positioned to make implementation decisions based on the results we generate.

5. Deliverables and Dissemination Plan

Our deliverables and dissemination plan have two purposes: To provide information for operational decisions by TPMG and KFH, and to establish our reputation as leaders in Desktop Medicine and Pharmacy Services through publication. Specific deliverables and plans include:

- The PI will prepare a presentation prior to study initiation to support conversations with leaders of service areas that will be included.
- Soon after the analysis of computerized data is completed, we will create an internal report for Drs. [name] and [name] to share via presentation to the appropriate chiefs and other operational leadership groups.
- The analysis of clinician and patient data will be completed after this, and we will update the internal report to support a follow-up communication.
- We will write a manuscript for submission to a peer-reviewed journal to share our findings with health care leaders in the U.S. and beyond.

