Appendix A. Power calculations

Est. # eligible, per week (7 per day to pediatrics) **35**

Est. # eligible over: 9 weeks **315**

of facilities (clusters) **63**

Cluster size **5**

Least detectable
differences

Assumptions: Power = 0.80, alpha = 0.05

For proportions, P0=0.50

ICC = 0.01 0.657

ICC = 0.03 0.663

ICC = 0.05 0.679

For proportions, P0 = 0.80

ICC = 0.01 0.912

ICC = 0.03 0.915

ICC = 0.05 0.919

Surveys	
Response rate	0.6
N	189
N per cluster	3

For means,

ICC = 0.01 0.322 0.412

ICC = 0.03 0.334 0.42

ICC = 0.05 0.346 0.427

Ref: University of Aberdeen cluster sample size calculator

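### Section 4.8 gives the Aim 3 survey 80% power for an effect of .037 SD; the plan's own inputs and Appendix A give 0.42, and the survey sample is described inconsistently

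*Combined protocol and SAP*

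**What the plan says.** The Aim 3 paragraph of section 4.8 (Sample size and power) concerns perceived effectiveness and quality of care, treated as continuous 5-point scores. On the number approached it says "We will attempt to survey all 315 parents in each of the two study groups". It assumes a 60% response rate, "for a completed sample of 189 across groups". It then states "This sample size will yield 80% power to detect effect sizes of .037 (relative to a standard deviation of 1" and concludes that "the survey will have good power to identify medium sized differences in perceived effectiveness and quality of care".

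Three other places bear on this:

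- Earlier in section 4.8, for the trial as a whole: "the estimated sample size is 315 patients, or an average of 5 patients in each of the 63 clusters".
- Appendix A lists 189 surveys at 3 per cluster. Its row for means at the expected ICC reads "ICC = 0.03 0.334 0.42": the first value is for 5 patients per cluster and the second for the survey.
- Section 4.5 (Data collection) describes "surveying a sample of parents selected at random in both the Pharmacist Care and PCP Care groups".

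Section 4.6 sets the test: "Tests of significance will be two-tailed with an alpha of .05".

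**The concern.** An effect of .037 SD is very small, and a survey of 189 people in 63 clusters cannot plausibly detect it with 80% power. The figure also conflicts with the sentence after it, which speaks of medium-sized differences, and with Appendix A. The number of parents to be approached conflicts with the total used elsewhere in the plan, and the choice between all parents and a random sample is left open.

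Parent satisfaction is a named aim and a listed secondary outcome, and the example hypothesis for Aim 3 in section 1 is comparable satisfaction in the two groups. A reader who believed the survey could detect .037 SD might take a non-significant result as strong evidence of comparability, when a difference of nearly 0.4 SD could be missed. Uncertainty about who is surveyed also leaves the response-rate denominator unclear.

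**Working it through.** **Inputs**

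- Two-tailed alpha 0.05 (section 4.6) and power 80% (section 4.8), so z = 1.960 + 0.842 = 2.8016 before rounding.
- K = 63 facilities and expected ICC 0.03 (section 4.8).
- N = 189 completed surveys, m = 189/63 = 3 per facility (section 4.8 and Appendix A).
- SD = 1. The 32:31 split of facilities is treated as equal; using the exact split changes the results only in the fourth decimal.

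**Formula**

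DEFF = 1 + (m − 1) × ICC, and detectable effect = z × √(4 × DEFF / N).

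**Reproducing the plan's own figures**

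| ICC | N = 315, m = 5 | Appendix A | N = 189, m = 3 | Appendix A |
|---|---|---|---|---|
| 0.01 | 0.322 | 0.322 | 0.412 | 0.412 |
| 0.03 | 0.334 | 0.334 | 0.420 | 0.42 |
| 0.05 | 0.346 | 0.346 | 0.427 | 0.427 |

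All six values for means agree, so this is the plan's method. The match also identifies the second column as the survey column, although its heading is not legible in the text available.

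**The Aim 3 figure**

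- DEFF = 1 + 2 × 0.03 = 1.06.
- Standard error = √(4 × 1.06 / 189) = 0.1498.
- Detectable effect = 2.8016 × 0.1498 = 0.420.
- The stated .037 is smaller by a factor of 0.42/0.037, about 11.

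**Power at particular effects (N = 189, ICC 0.03, two-sided)**

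- 0.037: 0.037/0.1498 = 0.247. Power = Φ(0.247 − 1.960) + Φ(−0.247 − 1.960) = 0.043 + 0.014 = 0.057.
- 0.37: 0.37/0.1498 = 2.470. Power = Φ(0.510) = 0.695.
- 0.42: power = 0.801.

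**Could .037 be reached, or be 0.37 with a slipped decimal?**

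- As N grows with 63 facilities fixed, the detectable effect tends to 2.8016 × √(4 × 0.03/63) = 0.122. At ICC 0.03, no number of responses reaches 0.037.
- With no clustering at all, 0.037 needs 4 × (2.8016/0.037)², about 22,934 responses.
- With ICC 0, 189 responses detect 2.8016 × √(4/189) = 0.408, still above 0.37.
- At ICC 0.03, solving 4 × [1 + (N/63 − 1) × 0.03]/N = (0.37/2.8016)² gives N = 249.7, so 250 responses are needed for 0.37.
- A one-sided 0.05 test at N = 189 gives (1.645 + 0.842) × 0.1498, about 0.37, but section 4.6 specifies two-tailed tests.

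**The survey sample**

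- 315 in total: 315 × 0.6 = 189, as stated, or 3 per facility, as in Appendix A.
- 315 in each group: 630 × 0.6 = 378, or 6 per facility. DEFF = 1.15 and the detectable effect is 2.8016 × √(4 × 1.15/378) = 0.309. This agrees with neither the 189 nor the 0.42.

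**The case against.** The strongest reply is that this is a reporting slip on a secondary outcome. Appendix A holds the right value, the next sentence says the effect is medium-sized, and a reader can recover the total of 315 from the 60% and the 189. All of that stands, and it keeps the point modest. It does not make the sentence right: section 4.8 is where the power is stated, and the obvious mental correction to 0.37 is also wrong.

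Four narrower points deserve weight.

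- The description as medium-sized fits 0.37 as well as 0.42. The case therefore rests on the arithmetic and not on that phrase, and the origin of .037 is unknown.
- Appendix A should be called correct only for means. In its proportions block, the entry for P0 = 0.50 at ICC 0.05 is 0.679. The same approach (DEFF 1.20, 157.5/1.20 = 131.25 effective patients per arm) gives about 0.668. That entry plays no part in Aim 3.
- The value 0.42 applies to a difference in means. Section 4.6 plans linear mixed regression for satisfaction but also says that responses will be collapsed to a binary variable. A binary comparison would need its own calculation. The power sentence at issue treats the score as continuous, so the correction to that sentence is unaffected.
- The 189 rests on 9 weeks of requests at the pilot rate for secure messages, whereas section 4.1 sets a 7-week period and refill authorization requests only. If the pilot rate carried over (an assumption), 35 × 7 = 245 requests would yield 245 × 0.6 = 147 responses. DEFF would be 1.04 and the detectable effect 2.8016 × √(4 × 1.04/147) = 0.47. This supports tying the corrected figure to its N; it does not rescue .037.

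**Conclusion.** The concern holds. On the plan's own inputs, the survey has 80% power for a difference of 0.42 SD, not .037, and its power at .037 is about 6%. The result moves little with the ICC, from 0.412 at 0.01 to 0.427 at 0.05, and no reading of the decimal point reconciles the text with a two-tailed test on 189 responses. The statement of 315 parents in each group contradicts both the total of 315 and the 189 responses derived from it, and sections 4.5 and 4.8 disagree on whether all parents or a random sample will be surveyed.

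The conclusion assumes equal arms, a continuous score with SD 1, 3 responses in each of 63 facilities and ICC 0.03, all as in the plan apart from rounding the 32:31 split. It should be fixed, but the consequences are limited: the survey values in Appendix A are right, interval estimates are planned, and no analysis depends on the misstated number. For interpretation, the 95% interval for the group difference would extend about 1.96 × 0.1498 = 0.29 SD on either side of the estimate.

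**What to change.** In the Aim 3 paragraph of section 4.8:

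- Replace .037 with 0.42 and give its basis: 189 responses, 63 facilities, ICC 0.03, two-tailed alpha 0.05, and a difference in mean scores.
- State that the 315 parents are the total across both groups. If 315 per group was in fact intended, the completed sample, cluster size and detectable effect must all be restated (378, 6 and 0.31), in Appendix A as well.
- Use one survey frame in sections 4.5 and 4.8 and Appendix A: either all parents or a random sample of stated size.
- If the expected number of requests over the 7-week period differs from 315, recompute the detectable effect from that number.

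The first three changes are wording only, provided 315 is the total; the last is a one-line recalculation. None affects enrolment, outcomes or the analysis.
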